8.3 Adverse Events

The definitions of an AE or SAE can be found in Appendix 3 (Section 10.3).

Adverse events can be reported by the participant (or, when appropriate, by a caregiver, surrogate, or the participant's legally authorized representative).

The Investigator and any designees are responsible for detecting, documenting, and recording events that meet the definition of an AE or SAE and remain responsible for following up AEs that are serious, considered related to the study treatment or study procedures, or that caused the participant to discontinue the study treatment or MG0003 (see Section 7).

8.3.1 Time period and frequency for collecting AE and SAE information

All SAEs will be collected from the signing of the ICF until the EOS visit at the time points specified in the Schedule of Activities (Section 1.3).

All AEs will be collected from the signing of the ICF until the EOS visit at the time points specified in the Schedule of Activities (Section 1.3).

All SAEs will be recorded and reported to the sponsor or designee within 24 hours, as indicated in Appendix 3 (Section 10.3). The Investigator will submit any updated SAE data to the sponsor within 24 hours of it being available.

The Investigator is specifically requested to collect and report to UCB (or its representative) any SAEs (even if the Investigator is certain that they are in no way associated with the study medication), up to 30 days from the end of the study for each participant, and to also inform study participants of the need to inform the Investigator of any SAE within this period. Serious AEs that the Investigator thinks may be associated with the study medication must be reported to UCB regardless of the time between the event and the end of the study.

The method of recording, evaluating, and assessing causality of AE and SAE and the procedures for completing and transmitting SAE reports are provided in Appendix 3 (Section 10.3).

8.3.2 Method of detecting AEs and SAEs

Care will be taken not to introduce bias when detecting AEs and/or SAEs. Open-ended and non-leading verbal questioning of the participant is the preferred method to inquire about AE occurrences.

8.3.3 Follow-up of AEs and SAEs

After the initial AE/SAE report, the Investigator is required to proactively follow each participant at subsequent visits/contacts. All AEs and SAEs, (and non-serious AEs of special interest and adverse events of special monitoring [AESM], as defined in Section 8.3.6 and Section 8.3.7, respectively), will be followed until resolution, stabilization, the Investigator determines that it is no longer clinically significant, the event is otherwise explained, or the participant is lost to follow-up (as defined in Section 7.3). Further information on follow-up procedures is given in Appendix 3 (Section 10.3).

8.3.4 Regulatory reporting requirements for SAEs

Prompt notification (24 hrs) by the Investigator to the sponsor of an SAE is essential so that legal obligations and ethical responsibilities towards the safety of participants and the safety of a study treatment under clinical investigation are met.

The sponsor has a legal responsibility to notify both the local regulatory authority and other regulatory agencies about the safety of a study treatment under clinical investigation. The sponsor will comply with country-specific regulatory requirements relating to safety reporting to the regulatory authority, Institutional Review Boards (IRB)/Independent Ethics Committees (IEC), and investigators.

Investigator safety reports must be prepared for suspected unexpected serious adverse reactions according to local regulatory requirements and sponsor policy and forwarded to investigators as necessary.

An Investigator who receives an Investigator safety report describing an SAE or other specific safety information (eg, summary or listing of SAEs) from the sponsor will review and then file it along with the Investigator's Brochure and will notify the IRB/IEC, if appropriate, according to local requirements.

8.3.5 Pregnancy

Details of all pregnancies in female participants and, if indicated, female partners of male participants will be collected after the start of study treatment and until 3 months after the last dose.

If a pregnancy is reported, the Investigator must immediately inform the sponsor within 24 hours of learning of the pregnancy and should follow the procedures outlined in Appendix 4 (Section 10.4).

The study participant must be withdrawn from the study as soon as pregnancy is known (by positive pregnancy test), and the following should be completed:

- The study participant should return for an early discontinuation (PEOT) visit.

Abnormal pregnancy outcomes (eg, spontaneous abortion, fetal death, stillbirth, congenital anomalies, ectopic pregnancy) are considered SAEs.

8.3.6 Adverse events of special interest

An AE of special interest (AESI) is any AE that a regulatory authority has mandated be reported on an expedited basis, regardless of the seriousness, expectedness, or relatedness of the AE to the administration of a UCB product/compound. An AESI should be immediately reported within 24 hrs to UCB. Potential Hy's Law, defined as ALT or AST $\geq 3 \times \text{ULN}$ with coexisting $\geq 2 \times \text{ULN}$ total bilirubin in the absence of $\geq 2 \times \text{ULN}$ ALP, with no alternative explanation for the biochemical abnormality (ie, without waiting for any additional etiologic investigations to have been concluded). Follow-up information should then be reported if an alternative etiology is identified during investigation and monitoring of the participant.

All AESIs will follow the SAE recording and reporting procedures as indicated in Appendix 3 (Section 10.3).

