7.1 Discontinuation of Study Medication

7.1.1 Liver Chemistry Stopping Criteria

Discontinuation of study treatment for abnormal liver function should be considered by the Investigator when a study participant meets one of the conditions outlined in [Figure 7-1](#) and [Figure 7-2](#), or if the Investigator believes that it is in the best interest of the study participant.

[figure not shown]
The study participant should follow the visit schedule as described in the protocol and the eCRF be completed accordingly.

Figure 7-1: Liver Chemistry Stopping Criteria and Increased Monitoring Algorithm

ALT=alanine transaminase; AST=aspartate aminotransferase; INR=international normalized ratio; SAE=serious adverse event; ULN=upper limit of normal

Figure 7-2: Liver Chemistry Increased Monitoring Algorithm with Continued Study Intervention for Participants with ALT $\geq 3xULN$ but $\leq 8xULN$

ALT=alanine transaminase; AST=aspartate aminotransferase; bili=bilirubin; INR=international normalized ratio; SAE=serious adverse event; ULN=upper limit of normal

Specific assessments and follow-up actions for potential drug-induced liver injury are provided in Appendix 6 (Section 10.6).

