
NOTES :
 
^a Details of liver chemistry stopping criteria and required actions and follow-up assessments after liver stopping or monitoring event are given in Section 10.6 and Appendix 6. All events of ALT $\geq 3xULN$ and bilirubin $\geq 2xULN$ (>35% direct bilirubin) or ALT $\geq 3xULN$ and international normalized ratio (INR) >1.5, if INR measured, may indicate severe liver injury (possible Hy's Law) and must be reported as an SAE (excluding studies of hepatic impairment or cirrhosis).
 
^b Local urine testing will be standard for the protocol unless serum testing is required by local regulation or IRB/IEC.
	

Investigators must document their review of each laboratory safety report.

Laboratory/analyte results that could unblind the study will not be reported to investigative sites or other blinded personnel until the study has been unblinded.

10.3 Appendix 3: Adverse Events – Definitions and Procedures for Recording, Evaluating, Follow-up, and Reporting

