10.6 Appendix 6: Liver Safety – Suggested Actions and Follow-up Assessments

Participants with potential drug-induced liver injury must be assessed to determine if study medication must be discontinued. In addition, all concomitant medications and herbal supplements that are not medically necessary should also be discontinued.

Investigators should attempt to obtain information on study participants in the case of study medication discontinuation to complete the final evaluation.

Study participants with potential drug-induced liver injury should not be withdrawn from the study until investigation and monitoring are complete. All results of these evaluations and observations, as well as the reason(s) for study medication discontinuation and/or participant withdrawal (if applicable), must be recorded in the source documents. The CRF must document the primary reason for discontinuation of study medication.

A specific monitoring plan must be agreed between the UCB study physician and the Investigator for study participants who have ALT >5 ULN. The monitoring plan should include any necessary follow-up assessments (until resolution of the abnormal lab values).

Table 10–2: Liver Chemistry Stopping Criteria and Follow-Up assessments

Liver Chemistry Stopping Criteria	
ALT-absolute	ALT ≥8xULN
ALT Increase	ALT ≥5xULN but <8xULN persists for ≥2 weeks ALT ≥3xULN but <5xULN persists for ≥4 weeks
Bilirubin^{a, b}	ALT ≥3xULN and bilirubin ≥2xULN (>35% direct bilirubin)
INR²	ALT ≥3xULN and international normalized ratio (INR) >1.5, if INR measured
Cannot Monitor	ALT ≥5xULN but <8xULN and cannot be monitored weekly for ≥2 weeks ALT ≥3xULN but <5xULN and cannot be monitored weekly for ≥4 weeks
Symptomatic^c	ALT ≥3xULN associated with symptoms (new or worsening) believed to be related to liver injury or hypersensitivity
Suggested Actions and Follow up Assessments	
Actions	Follow Up Assessments

 • Immediately discontinue study medication. • Report the event to UCB within 24 hours. • Complete the liver event case report form (CRF), and complete a serious adverse event (SAE) data collection tool if the event also met the criteria for an SAE.^b 	
 • Viral hepatitis serology^d • Obtain INR and recheck with each liver chemistry assessment until the transaminases values show downward trend • Only in those with underlying chronic hepatitis B at study entry (identified by positive hepatitis B surface antigen,

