---	---

- a. Serum bilirubin fractionation should be performed if testing is available. If serum bilirubin fractionation is not immediately available, discontinue study medication if ALT $\geq 3xULN$ **and** bilirubin $\geq 2xULN$. Additionally, if serum bilirubin fractionation testing is unavailable, **record the absence/presence of detectable urinary bilirubin on dipstick** which is indicative of direct bilirubin elevations suggesting liver injury.
- b. All events of ALT $\geq 3xULN$ **and** bilirubin $\geq 2xULN$ (>35% direct bilirubin) or ALT $\geq 3xULN$ **and** INR >1.5 may indicate severe liver injury (**possible ‘Hy’s Law’**) **and must be reported as an SAE (excluding studies of hepatic impairment or cirrhosis)**. The INR measurement is not required and the stated threshold value will not apply to participants receiving anticoagulants.
- c. New or worsening symptoms believed to be related to liver injury (such as fatigue, nausea, vomiting, right upper quadrant pain or tenderness, or jaundice) or hypersensitivity (such as fever, rash or eosinophilia).
- d. Includes: Hepatitis A immunoglobulin M (IgM) antibody; HBsAg and HBcAb; hepatitis C RNA; cytomegalovirus IgM antibody; Epstein-Barr viral capsid antigen IgM antibody (or if unavailable, heterophile antibody or monospot testing); and hepatitis E IgM antibody.
- e. If hepatitis delta antibody assay cannot be performed, it can be replaced with a polymerase chain reaction (PCR) of hepatitis D RNA virus (where needed) [Le Gal et al, 2005]. Record the date/time of the PK blood sample draw and the date/time of the last dose of study medication prior to the PK blood sample draw on the CRF. If the date or time of the last dose is unclear, provide the participant’s best approximation. If the date/time of the last dose cannot be approximated OR a PK sample cannot be collected in the time period indicated above, do not obtain a PK sample. Instructions for sample handling and shipping are in the IMP Handling Manual.

Table 10–3: Liver chemistry increased monitoring criteria with continued study medication

Liver Chemistry Increased Monitoring Criteria	
Criteria	Actions

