
ALT $\geq 5xULN$ and $< 8xULN$ and bilirubin $< 2xULN$ without symptoms believed to be related to liver injury or hypersensitivity, and who can be monitored weekly for 2 weeks.
 
OR
 
ALT $\geq 3xULN$ and $< 5xULN$ and bilirubin $< 2xULN$ without symptoms believed to be related to liver injury or hypersensitivity, and who can be monitored weekly for 4 weeks.
	
 • Notify the Sponsor Medical Monitor within 24 hours of learning of the abnormality to discuss participant safety. • Participant can continue study medication. • Participant must return weekly for repeat liver chemistry tests (ALT, AST, alkaline phosphatase, bilirubin) until the abnormalities resolve, stabilize, or return to baseline. • If at any time, the participant meets liver chemistry stopping criteria, proceed as described in Section 7.1.1. • If ALT decreases from ALT $\geq 5xULN$ and $< 8xULN$ to $\geq 3xULN$ and $< 5xULN$, continue to monitor liver chemistries weekly. • If, after 4 weeks of monitoring, ALT $< 3xULN$ and bilirubin $< 2xULN$, monitor participants twice monthly until liver chemistry tests resolve, stabilize, or return to baseline.

ALT=alanine aminotransferase; AST=aspartate aminotransferase; ULN=upper limit of normal

10.7 Appendix 7: Medical Device Incidents – Definition and Procedures for Recording, Evaluating, Follow-up, and reporting

Not applicable.

This document cannot be used to support any marketing authorization application and any extensions or variations thereof.

PUBLIC COPY

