8.2.6 Assessment and management of TB and TB risk factors	LTBI, active TB or other NTMB identified during study: The following sentence has been deleted; “If a TB specialist excludes an active TB infection, the subject can restart the study medication no earlier than 4 weeks after the start of an appropriate prophylactic therapy”	There is no restart procedure in place for participants with an active TB infection.
8.3 Adverse Events	The following sentence was amendment to include “study treatment in place of rozanolixizumab: “AEs that are serious, considered related to the study treatment or study procedures, or that caused the participant to discontinue the study treatment or MG0003.	This change was made to include any AE cases that included study participants receiving placebo.

Section # and Name	Description of Change	Brief Rationale
8.3.6 Adverse events of special interest	Measurements for ALT, and bilirubin or ALT were amended to: 3xULN ALT and $\geq 2xULN$ bilirubin ($>35\%$ direct bilirubin) or ALT $\geq 3xULN$ and international normalized ratio (INR) >1.5 , if INR measured.	Original wording was inconsistent with Section 10.2, Appendix 2 Clinical Laboratory Tests.
8.3.7 Adverse events of interest	This section has renamed to “Adverse events of special monitoring” New information to include that AEs of hypersensitivity reactions and infused-related reactions will be monitored by the investigators	Terminology change for consistency. Harmonize the AEs of special monitoring across the rozanolixizumab Phase 3 clinical program.
8.3.8 Treatment-emergent adverse events	A new subsection has been added.	To provide a clear definition of a treatment-emergent adverse event.
8.5 Treatment of Overdose	Definition of overdose was amended: Any dose increase of 10% or greater from the assigned dose for each administered dose of IMP per week should be considered, irrespective of the weight tier band.	The change was made to provide further clarification on the definition of overdose.
8.6 Pharmacokinetics and antidrug antibodies	Use of samples for establishing assay parameters added.	To be consistent with the ICF and other Rozanolixizumab protocols. Further, to remove detail redundancies covered in the laboratory manual.
8.7 Pharmacodynamics	Additional information has been added on limited testing to the positive antibody.	To be consistent with the ICF and other rozanolixizumab protocols. Further, to remove detail redundancies covered in the laboratory manual.

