10.3.1 Potential drug-induced liver injury

The number and percentage of study participants who meet one or more of the following potential drug-induced liver injury (pDILI) criteria will be summarized by treatment group and RLZ total:

- Participants with at least one post-Baseline liver laboratory assessment
- Incidence of potential hepatotoxicity with symptoms potentially associated with hepatitis or hypersensitivity
- Incidence of potential hepatotoxicity with no symptoms potentially associated with hepatitis or hypersensitivity
- Laboratory criteria for pDILI:
 - (AST or ALT > 3 x ULN) and TBL > 1.5 x ULN
 - (AST or ALT > 3 x ULN) and TBL > 2 x ULN
 - (AST or ALT > 3 x ULN) and TBL > 2 x ULN and ALP < 2 x ULN (Hy's Law)

In order to meet the above criteria, a study participant must experience the elevation in bilirubin and ALT or AST (and the absence of the ALP elevation) at the same visit. For example, a study participant who experiences a > 2x ULN elevation of bilirubin at one visit and a > 3x ULN

elevation in ALT (or AST) at a subsequent visit has not fulfilled the Hy's law criteria. If participant meets part of one criterion but at least one parameter is unknown, then he/she should not be considered for meeting the criterion.

Additional analyses for liver function tests (LFTs) will be performed to assess the potential for liver toxicities in accordance with the United States Food and Drug Administration guidelines. Per guidelines, the following criteria will be used to define levels of LFT elevation:

- Aspartate aminotransferase (AST): >3 x ULN, >5 x ULN, >8 x ULN, >10 x ULN, >20 x ULN
- Alanine aminotransferase (ALT): >3 x ULN, >5 x ULN, >8 x ULN, >10 x ULN, >20 x ULN
- AST or ALT: >3 x ULN, >5 x ULN, >8 x ULN, >10 x ULN, >20 x ULN
- Total bilirubin (TBL): >1.5 x ULN, >2 x ULN
- Alkaline phosphatase (ALP) >1.5 x ULN

A listing will also be provided for study participants who meet at least one of the above criteria. All results obtained at that visit for the specified parameters will be displayed.

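### Potential Hy's Law has two definitions in the protocol, and an AST-driven case under Section 8.3.6 meets no stopping criterion in Table 10-2 (minor, safety only)

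*Protocol*

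**What the plan says.** **Protocol 8.3.6** gives the AESI definition: "Potential Hy's Law, defined as ALT or AST" at or above 3xULN, with total bilirubin at or above 2xULN, ALP below 2xULN and no alternative explanation. Such events are reported within 24 hours and follow the SAE procedures.

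**Protocol Appendix 2, note a**, covers ALT at or above 3xULN with either raised bilirubin or raised INR. It says of the INR route: "if INR measured, may indicate severe liver injury (possible Hy's Law) and must be reported as an SAE".

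**Protocol Appendix 6, Table 10-2**, has a bilirubin stopping row that reads "ALT ≥3xULN and bilirubin ≥2xULN (>35% direct bilirubin") and an INR row on ALT at or above 3xULN with INR above 1.5. Note b repeats the SAE duty under the label possible Hy's Law and adds: "The INR measurement is not required and the stated threshold value will not apply to participants receiving anticoagulants".

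**Protocol 7.1.3, item 7**, makes permanent discontinuation mandatory when the drug-induced liver injury discontinuation criteria are met.

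**SAP 10.3.1** has a Hy's Law row computed from same-visit laboratory values ("AST or ALT > 3 x ULN) and TBL > 2 x ULN and ALP < 2 x ULN (Hy's Law"). SAP 3.9 declares this definition as a change from the protocol. Under SAP 10.2.2, AESIs are counted from the investigator's answer on the CRF.

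**The concern.** A single clinical label carries two rules. One rule drives the AESI flag and matches the SAP row apart from strict inequalities. The other drives the mandatory SAE label and the tabulated stop. Two consequences follow.

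- A participant can have the event that the protocol singles out for expedited reporting and still meet no tabulated criterion for stopping the drug.
- The SAE label, the AESI flag and the SAP Hy's Law row can disagree for the same participant, depending on which section the investigator consulted.

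What is at stake is consistent handling of possible serious liver injury and a readable safety table.

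**Working it through.** There is no plan figure to reproduce. The check sets the rules side by side and runs cases through them.

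**The rules**

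| Element | Protocol 8.3.6 (AESI) | Appendix 2 note a / Appendix 6 note b (SAE and stop) | SAP 10.3.1 Hy's Law row |
|---|---|---|---|
| Transaminase | ALT or AST ≥3xULN | ALT ≥3xULN only | AST or ALT >3xULN |
| Bilirubin | ≥2xULN | ≥2xULN with >35% direct, or the INR route | >2xULN |
| INR | none | >1.5, if measured, replaces bilirubin | none |
| ALP | not ≥2xULN | no condition | <2xULN |
| Alternative explanation | must be absent | no condition | no condition |

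**Does any Table 10-2 criterion use AST?** The criteria are ALT absolute (1), ALT increase (2), bilirubin (1), INR (1), cannot monitor (2) and symptomatic (1). That makes 1 + 2 + 1 + 1 + 2 + 1 = 8, and all 8 require ALT at or above 3xULN.

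**Worked cases.** These are illustrative values in multiples of ULN, with no alternative explanation. INR is normal or not measured unless stated. In case 4 there are no symptoms, no persistence yet, and weekly monitoring is possible.

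| Case | Values | AESI (8.3.6) | Possible Hy's Law SAE (Appendices 2/6) | Table 10-2 stop at that visit | SAP Hy's Law row |
|---|---|---|---|---|---|
| 1 | AST 4, ALT 2, bilirubin 2.5, ALP 1 | yes | no | no | yes |
| 2 | ALT 5, AST 5, bilirubin 2.5 (50% direct), ALP 2.2 | no | yes | yes | no |
| 3 | ALT 4, AST 4, bilirubin 1, ALP 1, INR 1.8 | no | yes | yes | no |
| 4 | ALT 4, AST 1, bilirubin 3 (20% direct), ALP 1 | yes | no | no | yes |

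*Case 1.* AST 4 ≥ 3, bilirubin 2.5 ≥ 2 and ALP 1 < 2, so it is an AESI. ALT 2 < 3, so all 8 Table 10-2 criteria fail whatever the direct fraction, symptoms or INR. This is the gap.

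*Case 2.* ALT 5 ≥ 3 and bilirubin 2.5 ≥ 2 with 50% direct meet the appendix rule. ALP 2.2 ≥ 2 removes it from 8.3.6 and from the SAP Hy's Law row. It stays in the SAP row for transaminase >3xULN with bilirubin >2xULN.

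*Case 3.* ALT 4 ≥ 3 and INR 1.8 > 1.5 meet the appendix rule. Bilirubin 1 < 2 removes it from 8.3.6 and from the SAP row. The Schedule of Activities has INR only at Visits 1, 2 and 14, so this route depends mostly on unscheduled tests.

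*Case 4.* The 35% direct condition separates the rules. This case carries less weight, because exclusion criterion 23a treats a direct fraction below 35% as pointing to Gilbert's syndrome, which could be an alternative explanation. Persistence for 4 weeks would also bring it into Table 10-2.

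**Table 10-3.** Both of its triggers require bilirubin below 2xULN, while an AESI requires bilirubin at or above 2xULN. No AESI can fall there, whichever transaminase is raised, so the missing AST in Table 10-3 is not part of this gap.

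**The case against.** The strongest reply is that this is a labelling matter inside a protocol with several safety nets, and much of that stands.

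- *The names are not identical.* Section 8.3.6 says potential; the appendices say possible, for events that may indicate severe liver injury. A broader SAE trigger is not an error in itself. But 10.3.2 uses potential Hy's law as an SAE example, so the protocol does not keep the two terms apart.
- *A reader might infer that the protocol has no stopping rule at all for AST-driven cases.* The documents do not support that. Section 7.1.1 refers to Figure 7-1, which is not shown and lists AST among its abbreviations. An AST rule there cannot be excluded. Only the statement about Table 10-2 is established.
- *A reader might infer that such participants go unmanaged or unreported.* They do not. The investigator may stop the drug in the participant's interest (7.1.1), clinically significant laboratory abnormalities are to be repeated (8.2.4), and events are followed to resolution or stabilization (8.3.3). AESIs take the SAE route (8.3.6, 10.3.2), and Appendix 6 requires an assessment of whether the drug must be stopped.
- *A reader might infer that the SAP contradicts the protocol.* SAP 3.9 declares its definition, including the strict inequalities, as a change. Because AESIs are counted from the CRF, the AESI column above shows what the definition implies, not what the AESI table will necessarily show.
- *A reader might take the mismatched cases as a measure of frequency.* They are logical possibilities. The documents give no rate for any of them.

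**Conclusion.** The concern holds as a minor, safety-only inconsistency in the current protocol text. The two definitions disagree in both directions. An AST-driven AESI with ALT below 3xULN meets 0 of the 8 Table 10-2 criteria and is therefore not clearly covered by mandatory discontinuation under 7.1.3 item 7. ALT-plus-INR cases with bilirubin below 2xULN, and ALT-plus-bilirubin cases with ALP at or above 2xULN, carry the possible Hy's Law label without being AESIs or entering the SAP Hy's Law row.

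No case is hidden, and no efficacy, alpha or power result is affected. The conclusion is limited to the text and tables that can be read. If Figure 7-1 contains an AST stopping rule, the gap in stopping narrows to a disagreement between that figure and Table 10-2; the conflict between definitions remains.

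**What to change.** 1. In the bilirubin row of Table 10-2 and its note a, replace ALT with ALT or AST at or above 3xULN. Alternatively, state that any 8.3.6 AESI triggers the Table 10-2 stop and follow-up actions. The first option keeps the 35% direct condition of the row; the second closes case 1 at any direct fraction. Check Figure 7-1 against whichever is chosen. Do not add AST to the other Table 10-2 rows, which would create stops for isolated AST elevations, or to Table 10-3.
2. Reserve the term potential or possible Hy's Law for the 8.3.6 definition. Keep the bilirubin and INR criteria in Appendix 2 note a and Appendix 6 note b as stopping criteria that must still be reported as SAEs, described as events that may indicate severe liver injury. Substituting the 8.3.6 definition into those notes would risk dropping the automatic SAE duty for cases 2 and 3.
3. Leave the SAP 10.3.1 row as it is.

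The cost is a few lines of protocol wording and no new data. The downside is a few more stops for AST elevations with bilirubin at or above 2xULN, some possibly of muscle origin. Creatine phosphokinase is already a Table 10-2 follow-up test and helps to identify these.
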